9.4.2.1. Guidance for Cardiac Monitoring Following Treatment Initiation or Re-Initiation

Prerandomization (ie, pre-dose/baseline) vital signs (resting heart rate, systolic and diastolic BP, body temperature, and respiratory rate) will be used as the Baseline measurement. The pre-dose heart rate measurement will be used for comparison to the post-dose measurement. Subjects should receive the first dose of study treatment before 12:00 PM (noon).

First Dose Cardiac Monitoring

In-clinic cardiac monitoring, of at least 4 hours, will occur on Day 1 and will include the following ([Table 3](#)):

- Full baseline vital signs (heart rate, systolic and diastolic BP, body temperature, and respiratory rate) and a 12-lead ECG (taken with the subject in the supine position) will be assessed prerandomization.
- After the first dose of study treatment on Day 1, subjects must remain under observation in the clinic for at least 4 hours.
- At Hours 1, 2, and 3 (\pm 15 minutes) post-dose, the heart rate and systolic and diastolic BP will be assessed with the subject in the sitting position, with the time recorded. If the subject has a heart rate $<$ 50 bpm or if cardiovascular symptoms develop, then the subject should remain closely monitored, including 12-lead ECGs as clinically indicated, until the Hour 4 discharge assessment.
- At the Hour 4 (\pm 15 minutes) discharge assessment, heart rate and systolic and diastolic BP will be assessed with the subject in the sitting position and a 12-lead ECG (with the subject in the supine position) will be performed. Subjects may be discharged from the clinic after the 4-hour assessment if they meet the criteria

described in [Table 4](#). Subjects not meeting the discharge criteria will require extended monitoring as described below.

- Subjects experiencing a clinically relevant treatment-related symptomatic event (eg, chest pain, dizziness, palpitations, or syncope) associated with reduction of the heart rate or clinically relevant 12-lead ECG changes at any time during the 4-hour monitoring period must be discontinued from treatment ([Table 5](#)).

Table 3: Procedures to be Performed During the Monitoring Period

| Procedure | Pre-Dose | Hours 1, 2, 3 Post-Dose ^a | Hour 4 Post-Dose ^a |
|--------------------------------------------|----------|--------------------------------------|-------------------------------|
| Blood pressure and heart rate ^b | x | x | x |
| 12-lead ECG | x | | x |
| Assess discharge criteria | | | x |

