^a Measurements may be taken \pm 15 minutes of the scheduled time.

^b Heart rate is based on vital signs.

Table 4: Discharge Criteria After Cardiac Monitoring

| |
|--------------------------------------------------------------------------------------------------------------------------------------------------------------------------|
| Subjects will be released from the clinical site after dosing on Day 1 (but no sooner than 4 hours post-dose) when they fulfill the following discharge criteria: |
| 
 • Heart rate \geq 50 bpm or no more than 10 bpm lower than the pre-dose (baseline) value |
| 
 • No evidence of second-degree AV block or higher |
| 
 • No cardiac symptoms (eg, chest pain, dizziness, palpitations, lightheadedness, shortness of breath, or syncope) |

AV, atrioventricular

Note: Subjects should have written instructions on when to return to the clinic and a 24-hour contact phone number to call in the event of any new or worsened cardiovascular symptoms.

Extended Cardiac Monitoring

Subjects who do not meet discharge criteria at 4-hours post-dose will require extended cardiac monitoring:

- Vital signs will be assessed hourly and 12-lead ECG may be performed, as clinically indicated, until the subject meets the discharge criteria ([Table 4](#)).
- The Medical Monitor should be contacted if the subject does not meet the discharge criteria after \geq 4 hours of extended cardiac monitoring.
- Any subject who requires extended monitoring on Day 1 must return on Day 2 for the second dose and will be re-monitored as on Day 1. These subjects will be discontinued from study treatment if they do not meet the discharge criteria at 4 hours after the second dose. Extended cardiac monitoring should be continued until the subject meets the discharge criteria ([Table 4](#)).
- Subjects experiencing a symptomatic event (eg, chest pain, dizziness, palpitations, lightheadedness, shortness of breath, or syncope) at any time during the 4-hour monitoring period that is not associated with either a reduction in heart rate or clinically relevant change in 12-lead ECG, may be discharged provided they meet the

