- ^l Safety 12-lead ECGs with the subject in the supine position will be obtained prior to blood sample collection at Screening and prior to randomization on Week 0/Day 1 (baseline). Subjects with a 12-lead ECG showing a second or third-degree AV block, periods of asystole > 3 seconds, PR interval > 200 ms, QTcF ≥ 450 ms (men) or QTcF ≥ 470 ms (women) must not be randomized and should be considered a screen failure.
- ^m After dosing on Day 1, a 12-lead ECG with the subject in the supine position will be performed 4 hours (± 15 minutes) post-dose as described in Section 9.4.2.1. Details regarding additional ECGs are provided in Section 9.10.3.
- ⁿ Complete physical examination (including assessments of the skin, head, eyes, ears, nose, throat, neck, thyroid, lungs, heart, abdomen, back, lymph nodes, extremities, body weight, and height [height collected at Screening Visit only]) should be performed at screening and the Week 12/Early Termination visit. All other visits during the 12-Week Treatment Period should have a focused (complaints, signs, and symptoms) physical examination.
- ^o During the specified full physical examinations, specific systems (eyes, liver, skin and joints) will be examined for EIMs.
- ^p A PFT will include FEV₁ and FVC measurements. When available, DLCO measurements will also be performed (when DLCO is not available, sites should consult the Sponsor or Sponsor's delegate).
- ^q The Screening pulmonary function test (PFT) should be done within the 28-Day Screening period. PFTs should be performed ± 7 days during the study treatment period and posttreatment period (ie, 2-Week Follow-Up visit). PFTs occurring at the ET visit that are within 4 weeks of the last assessment (eg, Week 12), will only be required if clinically indicated. The 2-Week Follow-Up visit assessment is only required if clinically indicated. Details regarding additional PFTs are provided in Section 9.10.4.
- ^r The Screening OCT should be performed within the 28-Day Screening Period. Subsequent ophthalmoscopy with OCT should be performed ± 7 days of the study treatment period and posttreatment period (ie, 2-Week Follow-Up visit). OCTs occurring at the ET visit that are within 4 weeks of the last assessment (eg, Week 12) will only be required

if clinically indicated. The 2-Week Follow-Up visit assessment is only required if clinically indicated. Details regarding ophthalmoscopy and OCT assessments are provided in Section 9.10.5.

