6.4. Windowing Conventions

All scheduled study visits are defined relative to Study Day 1, the date of first dose. Scheduled visit windows are defined in Clinical Study Protocol APD334-301 Appendix 1. A windowing convention will be used to determine the analysis visit value for a given measurement and will be applicable for all by-visit summaries and analyses for efficacy and safety data. Refer to [Table 2](#) for specific visit windows.

Table 2: Visit Windows for Efficacy and Safety Analyses

For all efficacy (except endoscopy/MMS/histology), efficacy-related biomarkers, safety labs and vital signs	
Scheduled Study Visit (Protocol Scheduled Day)	Analysis Visit Window (Study Day)
Baseline	≤ 1
Week 0 (Day 1)	1
Week 0 (Day 2) ^a	2
Week 2 (Day 15 ± 3)	2 to 22, or 3 to 22 ^a
Week 4 (Day 29 ± 3)	23 to 43
Week 8 (Day 57 ± 3)	44 to 71
Week 12 (Day 85 ± 7)	72 to 99
Week 16 (Day 113 ± 7)	100 to 127
Week 20 (Day 141 ± 7)	128 to 155
Week 24 (Day 169 ± 7)	156 to 197
Week 32 (Day 225 ± 7)	198 to 253
Week 40 (Day 281 ± 7)	254 to 309
Week 48 (Day 337 ± 7)	310 to 351
Week 52 (Day 365 ± 14)	> 351
For endoscopy/MMS/histology/all composite endpoints that include an endoscopy component and/or RB/SF component, Physician’s Global Assessment, health-related quality of life, ECGs, OCT, and PFT	
Scheduled Study Visit (Protocol Scheduled Day)	Analysis Visit Window (Study Day)
Baseline	≤ 1
Week 0 (Day 1)	1
Week 0 (Day 2) ^a	2
Week 12 (Day 85 ± 7) ^{b,c}	66 to 113 (66 to 141 for assessments impacted by COVID-19 pandemic) ^d
Week 32 (Day 225 ± 7) [PFT only]	198 to 253 (198 to 281 for assessments impacted by COVID-19 pandemic) ^d
Week 52 (Day 365 ± 14) ^{b,d}	337 to 393 (337 to 421 for assessments impacted by COVID-19 pandemic) ^e

^a Applicable only for subjects who require extended monitoring on Day 2 for vital signs and ECGs.

^b Applicable to all Week 12 and Week 52 efficacy endpoints based on any component of Mayo clinic score, such as clinical remission and symptomatic remission. Protocol visit window for PFT and OCT at Week 12 is Day 85 ± 7 (FDA 2020).

^c Due to overlapping windows at Week 12 and Week 8/16, a hierarchical algorithm will be used for the mapping. Week 12 will always be mapped first, then assess records for the Week 8/16 mapping. If a scheduled Week 8 and 12, or Week 12 and 16 visits are both present in the same visit window, they will be mapped to separate visits (ie, Week 8 and Week 12 or Week 12 and Week 16).

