^d Due to overlapping windows in the RB/SF components at Week 52 and Week 48, a hierarchical algorithm will be used for the mapping. Week 52 will always be mapped first, then assess records for the Week 48 mapping. If a scheduled Week 48 and 52 visits are both present in the same visit window, they will be mapped to separate visits (ie, Week 48 and Week 52).

^e Assessments impacted by the COVID 19 pandemic are reported in the Date of Visit eCRF.

COVID-19, coronavirus disease 2019; ECG, electrocardiogram; eCRF, electronic case report form; MMS, modified Mayo Score; OCT, optical coherence tomography; PFT, pulmonary function test; RB, rectal bleeding; SF, stool frequency.

For cardiac remonitoring upon treatment reinitiation after Day 2, as manifested by more than 1 timed measurement in vital signs or electrocardiogram (ECG) parameters on the same collection date of an unscheduled visit, measurements will be mapped to analysis visit of Cardiac Remonitoring 1, Cardiac Remonitoring 2, etc. in the respective analysis dataset. For analysis, each timed measurement will be programmatically assigned to the nearest hourly timepoint (eg, Predose, 1-hour Postdose) based on their relationship to the dosing time on the same day. If the dosing date/time on the same day is missing, the timepoint will remain missing. Once mapped, these timed measurements from cardiac remonitoring visits will not be considered for any other analysis visit.

Windowing will be applied prior to any missing data calculations. The last nonmissing measurement taken prior to Day 1 (including unscheduled assessments) will be labeled as “Baseline”. Unless stated otherwise, data from all visits including scheduled, unscheduled, and ET visits will be eligible for allocation to an analysis visit. The 2-Week and 4-Week Follow-Up visits will not be included in the visit windows and will be summarized separately without any window applied.

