If one or more results for a variable are assigned to the same analysis visit, the result with the date closest to the protocol scheduled day will be used in the analysis, except for component subscores of MMS or TMS, in which case, the composite score and component subscores from the same date will be used in the analysis. If 2 measurements in the same analysis visit window are equidistant from the protocol scheduled study day, the earliest measurement will be used in the analysis. If multiple assessments are available on the same day, then the average of the assessment will be used in the analysis, except for laboratory and ECG data where the assessment at the earliest time of the same day will be used. If both central and local assessments of the same ECG or lab test are available on the same day, the central result will take precedence over the local result.

For the overlapping visit windows at Week 12 and Week 8/16, a hierarchical algorithm will be applied as follows: always map to the Week 12 study visit if the study day falls within the visit window of the Week 12 study visit, then assess the other records for the Week 8 or Week 16 study visit. The same algorithm will be used for Week 48 and Week 52, with Week 52 taking priority.

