18.4. ECG Evaluations

ECGs are recorded on a 12-lead ECG machine and read centrally. The following ECG parameters are reported for this study:

- HR (bpm)
- PR interval (ms)
- RR interval (ms)
- QRS interval (ms)
- QT interval (ms)
- QTcF interval (ms)
- Overall interpretation of ECG (Investigator's judgment):
 - Normal
 - Abnormal, Not Clinically Significant (Abnormal NCS)
 - Abnormal, Clinically Significant (Abnormal CS)

- Overall interpretation of ECG (central reader):
 - Normal
 - Abnormal NCS
 - Abnormal CS
- AV conduction abnormalities
 - First-degree AV block
 - Second-degree AV block type 1
 - Second-degree AV block type 2
 - Third-degree AV block

The following summaries will be provided for ECG data:

- Value and change from Baseline by visit (for quantitative measurements)
- Incidence of markedly abnormal values (defined in Section 18.4.1) and AV blocks by visit
- Shift in normal/abnormal NCS/abnormal CS in the overall interpretation (by investigator) from Baseline to end of treatment and to the worst-case post-Baseline
- Shift in markedly abnormal categories from Baseline to post-Baseline by visit

Listings of ECG results, including first dose cardiac monitoring, and discharge criteria for first dose cardiac monitoring will be provided.

A listing of all ECG assessments over time in subjects meeting markedly abnormal criteria will also be provided. For each subject, only ECG parameters ever meeting markedly abnormal criteria will be included.

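### The by-visit ECG value and change table in SAP 18.4 never uses the Day 2 Hour 4 ECG and, on the literal text of SAP 6.4, does not use the Day 1 Hour 4 ECG either

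*SAP*

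**What the plan says.** **ECGs collected.** Protocol 9.4.2.1 (First Dose Cardiac Monitoring and Table 3) states that before dosing on Day 1 "a 12-lead ECG (taken with the subject in the supine position) will be assessed prerandomization". Footnote m of the schedule in Protocol Appendix 1 adds: "After dosing on Day 1, a 12-lead ECG with the subject in the supine position will be performed 4 hours". Further ECGs may be taken as clinically indicated, both before Hour 4 and during extended monitoring. Subjects who needed extended monitoring "must return on Day 2 for the second dose and will be re-monitored as on Day 1".

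**Allocation to visits.** The second block of SAP Table 2 gives ECGs a Week 0 (Day 1) visit, which is Study Day 1, and a Week 0 (Day 2) visit, which is Study Day 2. Neither is divided by timepoint. The Day 2 row carries the footnote "Applicable only for subjects who require extended monitoring on Day 2 for vital signs and ECGs". Its Baseline row covers Study Day 1 and earlier, so Study Day 1 falls in two rows. Data from all visits can be allocated unless the SAP says otherwise.

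**Several ECGs on one day.** SAP 6.4 averages same-day assessments, "except for laboratory and ECG data where the assessment at the earliest time of the same day will be used". It maps timed ECGs to hourly timepoints only for remonitoring after Day 2.

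**Baseline.** SAP 6.2 defines it as the last non-missing value before the first dose, using date and time. SAP 6.4 has a different cut-off: "The last nonmissing measurement taken prior to Day 1 (including unscheduled assessments) will be labeled as" Baseline.

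**Outputs.** SAP 18.4 plans value and change from Baseline by visit for quantitative parameters, and "Incidence of markedly abnormal values (defined in Section 18.4.1) and AV blocks by visit". It has no ECG table by timepoint. SAP 6.3 states that summaries of abnormalities or worst-case values take in every measurement.

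**The concern.** Protocol 1.3 lists first-dose bradycardia and AV block among events reported with this drug class, and the Hour 4 ECG is the scheduled post-dose ECG on the dosing day. A rule that keeps the earliest ECG of the day favours the pre-dose one. The table that should show the change in PR and QTcF after the first dose could then hold values recorded before any drug was taken.

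PR is the most exposed parameter. SAP 18.4.1 sets markedly abnormal criteria for QT and QTcF only, and the first-dose ECG plots in SAP Section 20 cover heart rate only. The by-visit table is therefore PR's only quantitative summary. QTcF has category counts but no other summary of values and change.

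**Working it through.** There is no planned figure to reproduce. The check applies the selection rule to the scheduled ECGs.

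**Inputs.** From the documents: the ECG schedule, SAP Table 2, the earliest-time rule, and the two Baseline wordings. Assumed for illustration only: PR of 160 ms at screening, 158 ms Day 1 pre-dose, 170 ms Day 1 Hour 4, 165 ms Day 2 pre-dose and 172 ms Day 2 Hour 4.

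**Formula.** Change at a visit = (earliest ECG allocated to that visit) − (Baseline).

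| Baseline wording | Day 1 pre-dose ECG allocated to the Day 1 visit? | Day 1 record used and change | Day 2 record used and change |
|---|---|---|---|
| 6.2, before first dose | Yes (literal text) | Pre-dose: 158 − 158 = 0 ms | Pre-dose: 165 − 158 = +7 ms |
| 6.2, before first dose | No, Baseline row only | Hour 4: 170 − 158 = +12 ms | Pre-dose: 165 − 158 = +7 ms |
| 6.4, before Day 1 | Yes | Pre-dose: 158 − 160 = −2 ms | Pre-dose: 165 − 160 = +5 ms |

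Under the 6.4 wording the Day 1 pre-dose ECG is not the Baseline record, so there is no reason to remove it from the Day 1 visit.

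**Day 2.** The pre-dose ECG precedes Hour 4 and cannot be Baseline on either wording. The Day 2 Hour 4 value (172 ms, a change of 172 − 158 = +14 ms or 172 − 160 = +12 ms) is not selected in any row.

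**Day 1.** Hour 4 is selected only in the second row of the table, where the pre-dose ECG goes to Baseline alone. The SAP does not state that step. Even then, only the earliest remaining ECG is used. Later ECGs from extended monitoring are left out, and a clinically indicated ECG between dosing and Hour 4 would replace Hour 4.

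**AV block and markedly abnormal values.** SAP 6.3 sends by-visit summaries through the 6.4 windows, then says that abnormality summaries consider all measurements. The incidence table in 18.4 is both by visit and a summary of abnormalities. If the second sentence governs, post-dose ECGs count. The SAP does not say which sentence prevails for the by-visit rows.

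**First-dose heart rate.** SAP 18.5 tabulates value and change from pre-dose by Day 1 timepoint, minimum heart rate and time to minimum. SAP Section 20 plans two Day 1 scatter plots, each with a panel for the 4-hour ECG heart rate.

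**The case against.** The strongest reply is that a sensible programmer would treat the Day 1 pre-dose ECG as Baseline only. SAP 6.2 uses date and time, and both Table 2 and SAP Appendix 1 list Baseline and Day 1 as separate visits. A Day 1 row that is zero by construction is unlikely to have been intended. On that reading the earliest remaining Day 1 ECG is normally Hour 4. This stands as a plausible intention, but the text does not say so, and it does not rescue Hour 4 on Day 2.

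A reader might also infer that AV blocks seen only after dosing disappear from the tables. The documents do not support that. SAP 6.3 counts all measurements in abnormality summaries, SAP 18.4 plans a shift to the worst post-Baseline interpretation and listings that include first-dose monitoring, and SAP 18.1.5 has ECG data reviewed for events of special interest, among them AV conduction delay and bradycardia.

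Nor does it follow that first-dose effects vanish from the report. Heart rate is covered by timepoint under vital signs, and the Day 2 pre-dose ECG already follows the first dose, so that row is not free of drug effect.

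**Conclusion.** The point holds for one output, the by-visit table of value and change from Baseline for quantitative ECG parameters.

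- **Day 2:** the Hour 4 ECG is left out on every reading, provided the pre-dose ECG is taken as Protocol Table 3 schedules. This concerns only subjects monitored on Day 2, and the documents do not give their number.
- **Day 1:** on the literal text the Hour 4 ECG is left out for up to all 420 planned subjects (280 etrasimod, 140 placebo). The change is exactly zero with the 6.2 Baseline, or pre-dose minus screening with the 6.4 wording. The loss disappears if the pre-dose ECG is allocated to Baseline alone.
- **Most affected:** PR and QTcF. A PR increase can still show as first-degree AV block, and QTcF still has its category counts, if 6.3 governs those rows.

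This is more than missing detail, because a stated rule removes scheduled post-dose values and two programmers could produce different Day 1 PR tables from the same text. The Week 12 and Week 52 rows, with one scheduled ECG each, are not affected by this, and neither is any efficacy analysis. The stronger inferences, that AV-block incidence or all first-dose effects drop out of the report, are not supported.

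**What to change.** 1. In SAP 6.4, exempt Day 1 and Day 2 ECGs from the earliest-time rule. Change the Baseline wording from before Day 1 to before the first dose, to match 6.2. Remonitoring after Day 2 already has hourly mapping and needs no change.
2. In SAP 18.4, add a table of value and change from pre-dose for heart rate, PR and QTcF by timepoint, for Day 1 and Day 2. The timepoints are pre-dose, Hour 4, and the last ECG before discharge if that is later.
3. State that the by-visit incidence of AV block and markedly abnormal values on those days counts any post-dose ECG, in line with SAP 6.3.

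The cost is SAP wording and one more table. The ECGs are already collected under the protocol, so no new data are needed.

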6.5. Statistical Tests

The default significance level will be 0.05; confidence intervals (CIs) will be 95%, and all tests will be 2-sided, unless otherwise specified in the description of the analyses.

6.6. Common Calculations

For quantitative measurements:

- Change from Baseline = Test Value at Visit X – Baseline Value
- Percent change from Baseline = (Test Value at Visit X – Baseline Value) / Baseline Value × 100

- Proportion at Visit X = Number of subjects satisfying criteria at Visit X / Total number of subjects at Visit X

6.7. General Study Information

A general table with summary of study information will be generated, including the date of first subject signed informed consent form (ICF), the last subject visit date, and the database lock date. All analyses will be conducted using SAS® (v9.4 or later, SAS Institute Inc., Cary, NC).

7. DETERMINATION OF SAMPLE SIZE

Based on a 2-group Fisher’s exact test, a 1-sided significance level of 0.025, and a 2:1 randomization ratio, 420 total subjects (280 etrasimod, 140 placebo) are required to achieve 93.4% power to detect a difference of 13.5% in the primary endpoint of clinical remission at Week 52 between the etrasimod treatment group (23.5%) and the placebo treatment group (10.0%). With this sample size, there will be 96% power to detect a difference of 12.5% in the other primary endpoint of clinical remission at Week 12, assuming a placebo rate at 6.0%. The lower bound of overall power for both primary endpoints (as coprimary endpoints), is at least 90%; since the 2 primary endpoints are expected to be at least moderately, positively correlated, the actual overall power to reject both of their null hypotheses is likely to be greater than 90%. Workbook calculations from EAST® 6 statistical software are included below.

Design: Discrete Endpoint: Two-Sample Test - Parallel Design - Fisher's Exact

Test Parameters	
Design ID	Week 52 Clin Rem
Test Type	2-Sided
Specified α	0.05
Power	0.934
Sample Size (n)	420
Model Parameters	
Proportion Treatment (π_t)	0.235
Proportion Control (π_c)	0.1
$\delta = \pi_t - \pi_c$	
Under H0	0
Under H1	0.135
Allocation Ratio (n_t/n_c)	2

Sample Size Information

Sample Size (n)	420
Treatment (n _t)	280
Control (n _c)	140

Design: Discrete Endpoint: Two-Sample Test - Parallel Design - Fisher's Exact

Test Parameters	
Design ID	Week 12 Clin Rem
Test Type	2-Sided
Specified α	0.05
Power	0.96
Sample Size (n)	420
Model Parameters	
Proportion Treatment (π_t)	0.185
Proportion Control (π_c)	0.06
$\delta = \pi_t - \pi_c$	
Under H0	0
Under H1	0.125
Allocation Ratio (n_t/n_c)	2

⊖ **Sample Size Information**

Sample Size (n)	420
Treatment (n _t)	280
Control (n _c)	140

8. STATISTICAL CONSIDERATIONS**8.1. Multicenter Studies**

This study will be conducted by multiple investigators at multiple centers internationally. Randomization to treatment groups is stratified by:

- Naïve to biologic or JAK inhibitor therapy at study entry (Yes or No)
- Baseline corticosteroid use (Yes or No)
- Baseline disease activity (MMS: 4 to 6 or 7 to 9)

Data from all sites will be pooled and statistical analyses will not be adjusted for investigational site, country, or geographic region.

